2.5.1 Primary endpoint

The primary variable is change from baseline at Week 24 in the total score of 11 items included in the Mini-Mental State Examination (MMSE) for the FAS. Of note, the primary analysis will include all patients in the FAS population irrespective of the treatment regimen.

2.5.2 Statistical hypothesis, model, and method of analysis

The change from baseline in MMSE total score will be analyzed using a mixed model repeated measures (MMRM) model. The model will contain visit as a fixed effect, baseline MMSE score as a covariate and subject as a random effect. An unstructured covariance matrix should be used. The estimated mean change at Week 24 along with a two-sided 95% confidence interval and p-value will be tabulated and presented graphically. P-values will be used in descriptive manner.

Further, the MMSE total score and change from baseline will be summarized using standard descriptive statistics by visits.

In addition, the primary endpoint will be summarized and analyzed by subgroups specified in [Section 2.2.1.1](#).

The MMRM model of subgroup analysis will contain visit, subgroup (categories) and visit*subgroup as fixed effects, baseline MMSE score as a covariate and subject as a random effect. An unstructured covariance matrix should be used. The estimated mean change at Week 24 along with a two-sided 95% confidence interval and p-value will be presented. P-values will be used in descriptive manner. Figures will only be provided for selected subgroup analysis as specified in [Section 2.2.1.1](#).

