- Inadequate compliance with the ChE inhibitors at screening and baseline
- Inadequate treatment (efficacious dose was not reached or inadequate compliance) with the ChE inhibitors because of AEs except gastrointestinal (GI) symptoms (nausea and vomiting) at screening and baseline
- Patients with swallowing difficulties at screening and baseline

Further, a subgroup analysis will be presented for patients satisfying inclusion criteria

- 9-1 only, 9-2 only and both 9-1 and 9-2
- 9-1-1 only, 9-1-2 only, 9-1-3 only, and 9-1-1 and 9-1-3, and 9-1-2 and 9-1-3
- (9-1-1 or 9-1-2) versus (9-1-2 and 9-1-3) versus 9-1-3 only
- 9-1 versus 9-2
- (9-1 only) versus (9-1 and 9-2) or (9-2 only)
- (9-2 only) versus (9-1 and 9-2) or (9-1 only)

- Patients with concomitant use of memantine (yes/no)
- Patients satisfying treatment retention criteria as in Section 2.9.1 (yes/no)

Note: * items will also be illustrated using figures for the CSR.

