2.13 Interim analysis

Not applicable.

3 Sample size calculation

The sample size is determined as precision-based for the change from baseline in MMSE score at week 24. Ninety-seven patients will ensure that the half-width of 95% confidence interval for the change from baseline in MMSE score at week 24 would be 0.6, assuming SD=3.0 which is estimated from 1301, 1303 and 1403 studies. Assuming drop-outs, a total of 120 patients will be enrolled to achieve at least 97 evaluable patients.

4 Change to protocol specified analyses

The following are considered for the analysis which was not planned during the time of protocol development:

1. Rate of responses for change from baseline in MMSE total score has been provided based on Full Analysis Set, Per Protocol Set and subjects with 3-step titration.
A responder is defined as those patients whose MMSE total score has remained unchanged from baseline till Week 24 or, patients whose MMSE total score has improved at Week 24 compared to baseline.
2. For Neuropsychiatric Inventory (NPI), the value 0 is considered wherever N/A or Absent has been marked in the eCRF page.
3. Visit Window for discontinuations: The study does not have a pre-defined visit windows for the entire study period. However, correct visit re-mapping for the discontinued patients was performed for summarizing and listing the efficacy and safety variables by visits. The last records of the discontinued patients are re-mapped to the actual visit when they discontinued rather than the Visit 8/discontinuation as per the assessment schedule of the protocol. Re-mapping was done for the discontinued patients to the nearest planned visit as per their actual discontinuation/ assessment date for each variable.

The following efficacy assessments: MMSE, NPI-10, QOL-AD, J-CGIC and Modified Crichton Scale were re-mapped for the considered discontinued patients as described above.

Under safety assessment, Vitals were considered for re-mapping for the discontinuation patients as described above. For other safety assessments, this re-mapping had no impact.

5 Appendix

This appendix gives details about statistical methods in addition to the report text. All analyses will be performed by using SAS version 9.4.

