5.3.2 MMRM model of subgroup analysis

The MMRM model of subgroup analysis will contain visit, subgroup (categories) and visit*subgroup as fixed effects, baseline MMSE score as a covariate and subject as a random effect. An unstructured covariance matrix should be used.

```
proc mixed data = xxx ;
  class visit subgrcat subjid;
  model chg = visit subgrcat visit*subgrcat base / noint ddfm = KR alpha = 0.05;
  repeated visit /type = UN subject = subjid ;
  lsmeans visit*subgrcat /cl;
run;
```

where

chg: change from baseline in MMSE total score,

visit: study visits as per protocol assessment schedule,

subgrcat: subgroup categories,

visit*subgrcat: interaction effect of visit and subgrcat,

base: baseline MMSE score,

subjid: subject identifier.

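### The SAP sets criterion-9 subgroups against each other but plans only each group's own mean change and p-value, so the comparisons it names are not estimated (minor)

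*SAP*

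**What the plan says.** SAP 2.2.1.1 plans subgroup analyses of the MMSE change at Week 8 and Week 24. Among the rows built on inclusion criterion 9, four are worded as comparisons. Two of them read "9-1 only) versus (9-1 and 9-2) or (9-2 only" and "9-1-1 or 9-1-2) versus (9-1-2 and 9-1-3) versus 9-1-3 only". The other two set 9-1 against 9-2, and 9-2 only against the rest.

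SAP 2.5.2 fits visit, subgroup and their interaction, with baseline MMSE as covariate. The planned output for each subgroup is: "The estimated mean change at Week 24 along with a two-sided 95% confidence interval and p-value will be presented". It adds: "P-values will be used in descriptive manner".

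The code in SAP 5.3.2 is "model chg = visit subgrcat visit*subgrcat base / noint ddfm = KR alpha = 0.05", followed by "lsmeans visit*subgrcat /cl". It has no DIFF option and no ESTIMATE or CONTRAST statement. Neither document plans to report a between-subgroup difference or an interaction test.

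**The concern.** An LS-mean request with confidence limits tests each visit-by-subgroup mean against zero. (The text of 2.5.2 does not name the null hypothesis; this is read from the code.) A p-value against zero in group A and another in group B do not say whether A and B differ. The model could supply that difference, but the plan does not ask for it.

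Criterion 9 admits two kinds of patient: those not responding to oral cholinesterase inhibitors (9-1) and those with difficulty taking them (9-2). Whether their changes differ bears on how the pooled result is read. The criterion-9 rows are also marked for figures in the study report, which invites side-by-side reading.

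**Working it through.** **Inputs from the documents.** SAP section 3 gives a 95% CI half-width that "would be 0.6, assuming SD=3.0 which is estimated from 1301, 1303 and 1403 studies", and states that "a total of 120 patients will be enrolled to achieve at least 97 evaluable patients".

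**Assumptions not in the documents.** The true mean change (taken as equal in both subgroups, sign immaterial), the subgroup sizes (splits of 97), and a cut-off of p<0.05. The SAP attaches no decision to that cut-off.

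**Step 1: the plan's own figure.** n = (1.96 × 3.0 / 0.6)² = 9.8² = 96.04, rounded up to 97. It reproduces. The t-based version gives 99.

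**Step 2: one worked case.** Split 70/27, common true change 0.6, normal approximation.
- n = 70: SE = 3/√70 = 0.359; 0.6/0.359 = 1.67; chance of p<0.05 = 0.39.
- n = 27: SE = 3/√27 = 0.577; 0.6/0.577 = 1.04; chance of p<0.05 = 0.18.
- Exactly one significant: 0.39 × 0.82 + 0.61 × 0.18 = 0.43.

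The two groups are identical, yet 43% of trials would show one p-value below 0.05 and the other above it.

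**Step 3: the range.** With p₁ and p₂ the power of each one-sample t-test against zero (noncentral t), the chance of a split result is p₁(1−p₂) + p₂(1−p₁), in percent:

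| Split | 0 | 0.3 | 0.6 | 1.0 | 1.5 | 2.0 points |
|---|---|---|---|---|---|---|
| 48/49 | 9.5 | 18.8 | 40.0 | 47.0 | 13.6 | 1.0 |
| 24/73 | 9.5 | 19.0 | 42.6 | 59.3 | 35.3 | 12.2 |
| 10/87 | 9.5 | 19.3 | 46.2 | 75.2 | 70.5 | 53.1 |

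For 80/17 at 1.0 point, the normal approximation gives powers of 0.846 and 0.280, so 0.846 × 0.720 + 0.154 × 0.280 = 0.65. Over changes of 0.3 to 1.0 and splits of 49/48 to 80/17, the range is therefore roughly 20% to 65%. Simulating the Week 24 analysis with a baseline covariate gave similar values, for example 40% at 0.6 points with a 48/49 split.

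**Step 4: the missing contrast.** In the same simulation, testing the difference directly declared identical groups different in 4.3% to 5.4% of runs. The half-width of its 95% CI is 1.96 × 3.0 × √(1/n₁ + 1/n₂):
- 48/49: 1.2 points
- 24/73: 1.4 points
- 10/87: 2.0 points

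**Step 5: can the rows be contrasted as written?** Two of the four cannot.
- In 9-1 against 9-2, a patient may meet both, because protocol 4.1 allows it.
- In the three-way row, a patient meeting 9-1-2 and 9-1-3 also meets the first group, 9-1-1 or 9-1-2.

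One class variable cannot hold overlapping groups. The rows setting 9-1 only, or 9-2 only, against the rest are disjoint.

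**The case against.** **No objective asks about effect modification.** *Versus* may only name groups to be tabulated side by side, and protocol 3.2 says the study does not aim to prove superiority or non-inferiority. This limits the severity. It does not remove the mismatch: four rows are worded as comparisons and none is estimated.

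**The p-values are descriptive and CIs are shown.** This stands in part. A reader might infer that the tables leave nothing to compare except which p-values fall below 0.05. The documents do not support that. Each subgroup also gets a mean and CI, and for disjoint groups the difference can be approximated by hand. With a 49/48 split, half-widths of 0.84 and 0.85 combine to √(0.84² + 0.85²) = 1.19. But the plan leaves that work to the reader, and a descriptive p-value against zero still does not describe a difference.

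**PROC MIXED prints Type 3 tests by default.** True, but the SAP does not plan to report them. With MMSE scheduled at Weeks 8 and 24, the interaction test asks whether the subgroup difference changes between visits, not whether the Week 24 means differ.

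**The contrast cannot show that switching works differently in the two groups.** This stands in full. There is no comparator, and two of the 9-1 conditions select on a previous MMSE fall of at least 2 points. A difference in change therefore mixes any drug effect with natural decline and regression to the mean.

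**Many rows are defined after baseline.** This also stands: differences by titration regimen, reason for switching, compliance, retention or skin management would invite the same misreading.

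**Conclusion.** The point holds as a minor one. Followed as written, the SAP does not produce the between-group comparisons that 2.2.1.1 names, although the model it already fits could.

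The size depends on assumptions the documents do not supply. Split results for identical groups run from roughly 20% to 65% for true changes of 0.3 to 1.0 points and splits of 49/48 to 80/17. It is tempting to conclude that identical subgroups will generally look different. The figures do not support that without conditions: the chance is 9.5% at zero change and, with equal halves, about 14% at 1.5 points and 1% at 2.0. It stays high at large changes only when the split is very uneven. It also matters only if readers apply a p<0.05 cut-off that the SAP does not adopt.

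The primary analysis is untouched.

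**What to change.** 1. **SAP 2.2.1.1:** recode the overlapping rows into disjoint, baseline-defined categories: 9-1 only, 9-2 only, both; and likewise for combinations of 9-1-1, 9-1-2 and 9-1-3.
2. **SAP 5.3.2:** for baseline-defined subgroups, add ESTIMATE statements for the between-subgroup difference at Week 24 and at Week 8, or use DIFF and keep only same-visit pairs. Unrestricted DIFF on the interaction prints every pair: three subgroups at two visits make 6 cells and 6 × 5 / 2 = 15 pairs, of which only 3 + 3 = 6 are within a visit.
3. **SAP 2.5.2:** report each difference with its 95% CI, labelled exploratory, and drop or de-emphasise the within-subgroup p-values.
4. **Interpretation:** state that in a single-arm study this is a difference in change from baseline, not evidence of a different treatment effect.
5. **Groups defined after baseline** (titration regimen, reason for switching, compliance, retention, skin management): keep the descriptive summaries and make no contrasts.

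The cost is some recoding and programming, one table column and a few sentences. No new data are needed. The results will look less decisive, with half-widths of about 1.2 points for equal halves and up to 2.0 for a 10/87 split, but that imprecision is real and readers should see it.

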2.5.3 Handling of missing values/censoring/discontinuations

The primary analysis will be performed using a MMRM model, which assumes that missing data is missing at random (MAR) given the preceding observed data.

The discontinuations data has been handled as explained in Section 4, point 3. No other imputation methods will be considered.

2.5.4 Supportive analyses

As supportive to the primary analysis,

1. The change from baseline at Week 24 in MMSE total score analysis will be repeated using the similar MMRM analysis for (1) the Per protocol set and (2) the FAS 3-step set. These two analyses will separately present the results for patients who has 1-step and 3-step titrations respectively. Tables and corresponding figures will be presented.
2. The change from baseline to Week 24 in MMSE total score will be analyzed using a t-test for the FAS. The estimated mean change along with 95% confidence interval and two-

sided p-value will be presented. This analysis will be performed on study completers only without any imputation of missing data.

3. The change from baseline to Week 24 in MMSE total score imputed with last observation carried forward (LOCF) method will be analyzed using a t-test for the FAS. The estimated mean change along with 95% confidence interval and p-value will be presented.

The p-values obtained in the supportive analyses will be descriptive in nature.

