### **Per protocol Set (PP)**

The per protocol set will include all patients in FAS without any major deviations from the protocol procedures. The major protocol deviations will be specified prior to database lock.

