2.2 Analysis sets

Full Analysis Set (FAS)

The FAS will include all patients who received at least one dose of study treatment and had at least a baseline and any post-baseline assessment on treatment. This is the primary analysis population and will also be used for all efficacy analyses.

Per protocol Set (PP set)

The per protocol set will include all patients in the FAS who had only 1 step titration without any major deviations from the protocol procedures. The major protocol deviations will be specified prior to database lock.

Safety Set (SAF)

The safety set will consist of all patients who received at least one dose of drug and had at least one post-baseline safety assessment.

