2.6 Analysis of secondary objectives

2.6.1 Efficacy endpoints

All following secondary efficacy variables will be analyzed using the FAS, PP set and subset of patients in FAS who had 3-step titration

2.6.1.1 MMSE score at Week 8

The change from baseline to Week 8 in MMSE total score will be summarized descriptively and analyzed using the same MMRM model used for the primary analysis. The estimated mean change along with two-sided 95% confidence interval will be presented.

Same figure will present the estimates and 95% confidence intervals of change from baseline in MMSE score at both Week 8 and Week 24.

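### SAP 2.5.4 shows the per-protocol set as the 1-step result beside a 3-step set drawn from the FAS, so code-1 deviators are removed from the 1-step side only

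*SAP*

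**What the plan says.** SAP 2.5.4 item 1 repeats the Week 24 MMSE analysis "for (1) the Per protocol set and (2) the FAS 3-step set", and adds: "These two analyses will separately present the results for patients who has 1-step and 3-step titrations respectively". It promises tables and matching figures for both.

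Two other places use the same sets:

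- SAP 2.6.1: "All following secondary efficacy variables will be analyzed using the FAS, PP set and subset of patients in FAS who had 3-step titration". The only variable under that heading is MMSE at Week 8.
- SAP Section 4 point 1 gives the MMSE responder rate for the "Full Analysis Set, Per Protocol Set and subjects with 3-step titration".

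The PP set is defined differently in the two documents:

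- Protocol 9.1: "The per protocol set will include all patients in FAS without any major deviations from the protocol procedures".
- SAP 2.2: "The per protocol set will include all patients in the FAS who had only 1 step titration without any major deviations from the protocol procedures". SAP 2.1.1.1 says likewise that patients who cannot tolerate 1-step titration leave the PP analysis only.

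Protocol 3.1 and 5.1.1 let the investigator move a patient to 3-step titration and keep that patient in the study. Protocol 9.3 plans a count of those who switch. SAP 2.2 does not define the FAS 3-step set.

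**The concern.** A reader of the 2.5.4 tables and figures will take them as the 1-step and 3-step patients of the same trial population. They are not. One side has been cleaned of a class of protocol deviations and the other has not, so any visible gap between them mixes regimen with adherence to protocol. 1-step titration is the subject of the primary objective, so a figure carrying that label is likely to be quoted.

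The narrowed PP definition adds a second difficulty. The set is selected both on absence of major deviations and on a post-baseline event, the switch. A difference between PP and FAS therefore cannot be put down to deviations alone. The protocol treats the switch as permitted, while the SAP makes it a ground for leaving PP, and the SAP's own list of changes does not mention it.

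**Working it through.** **1. Which exclusions differ.** SAP Appendix 5.2, Table 2, gives the codes that remove a patient:

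| Set | Excluding codes |
|---|---|
| FAS | 0, 6, 8 |
| PP | 0, 1, 6, 8 |

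PP minus FAS leaves {1}. Codes 0, 6 and 8 act on both sets, and code 49 removes no one. Code 1 is the only category that acts on one side. It includes another cause of dementia (E01), donepezil above the entry limit (E21A), MMSE out of range (I07), prohibited medication (M01A, M01B) and low patch adherence (S10).

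**2. Do the two displays cover the FAS?** Under the SAP definitions the FAS splits into three groups:

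- 1-step without code 1: in PP, shown as 1-step.
- 1-step with code 1: in neither display.
- 3-step, with or without code 1: in the FAS 3-step set.

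PP plus FAS 3-step therefore falls short of the FAS by the second group.

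**3. What is available like for like.**

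- *MMSE change.* SAP 2.2.1.1 lists treatment regimen (1-step, 3-step) as a subgroup at Weeks 8 and 24, and SAP 2.5.2 gives its model. The population is not named there, but SAP 2.2 uses the FAS for all efficacy analyses. The item carries no asterisk, so no figure is planned for it. The figures come from 2.5.4.
- *Responder rate.* FAS, PP and 3-step only. There is no FAS 1-step result.
- *Other scales.* QOL-AD, NPI-10 and Modified Crichton are in SAP 2.8 and 2.9, with change from baseline summarised for the FAS. J-CGIC (SAP 2.10) names no set. Whether 2.6.1 reaches them is unclear.

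**4. Section 4.** It lists three changes: the responder rate, the NPI zero rule, and visit re-mapping for discontinued patients. The PP definition is not among them.

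**5. The plan's own precision figure.** Protocol 9.8 and SAP 3 give SD 3.0 and half-width 0.6:

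n = (1.96 × 3.0 / 0.6)² = 96.04, rounded up to 97. The stated figure is reproduced. It concerns the whole evaluable group and does not change.

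**6. Size of the shift.** Let q be the share of FAS 1-step patients with a code-1 deviation, and D the mean MMSE change of the non-deviators minus that of the deviators.

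- FAS 1-step mean = (1 − q) × non-deviator mean + q × deviator mean.
- PP mean = non-deviator mean.
- Shift = PP mean − FAS 1-step mean = q × D.

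This treats the model estimates as simple means. Neither q nor D is in the documents. Assuming q from 5% to 20% and D from 1 to 2 points:

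- Smallest: 0.05 × 1 = 0.05 points.
- Largest: 0.20 × 2 = 0.40 points.

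The shift favours the 1-step display if deviators do worse, and goes the other way if they do better.

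**7. Scale.** Assume also that 10%, 20% or 30% of 97 evaluable patients switch, with SD 3.0. Half-widths are t × 3.0/√n.

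| Switchers | FAS 1-step | PP (q = 5% to 20%) | In neither | FAS 3-step | 3-step half-width |
|---|---|---|---|---|---|
| 10% | 87 | 83 to 70 | 4 to 17 | 10 | 2.15 |
| 20% | 78 | 74 to 62 | 4 to 16 | 19 | 1.45 |
| 30% | 68 | 65 to 54 | 3 to 14 | 29 | 1.14 |

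The PP half-width runs from 0.66 to 0.82. At q = 20% it is 0.72 to 0.82, so a shift of 0.40 is about half of it (0.40/0.82 = 0.49; 0.40/0.72 = 0.56). At q = 5% it is 0.66 to 0.74, and a shift of 0.05 is under a tenth (0.05/0.66 = 0.08).

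**The case against.** The strongest reply is that the SAP already holds the fair comparison for the main endpoint, the regimen subgroup of 2.2.1.1. That stands, and it limits the point. For MMSE change the problem is which result is shown and labelled in 2.5.4, since a sound analysis exists alongside it.

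Second, the narrowing has a basis and is not hidden. Protocol 9.1 leaves major deviations to be specified before lock, Protocol 3.3 makes 1-step the rule where tolerated, and SAP Appendix 5.2 codes the 1-step schedule as S02, code 1. If S02 catches switchers, removing code 1 from the 3-step group would empty it, which explains why that set comes from the FAS. This stands as an explanation. It does not justify filtering one side only under regimen labels. SAP 2.2 also states 1-step titration as a condition separate from major deviations, so it adds to the protocol's definition.

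Third, the SAP says the results are presented separately, its code requests no difference between regimens, and p-values are descriptive. All true.

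Some stronger readings are tempting, and the documents do not support them:

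- *All deviators are removed from one side.* Only code 1 is.
- *A protocol-planned robustness check was lost.* The protocol defines a PP set but plans no analysis on it. Both of its sensitivity analyses use the FAS.
- *The change was concealed.* It is stated in SAP 2.1.1.1 and 2.2 and is missing only from Section 4.
- *Every secondary scale has an unbalanced 1-step/3-step display.* The reach of 2.6.1 is too unclear to say so.
- *PP contains only patients who tolerated 1-step.* SAP 2.2 asks for 1-step titration only, so on that wording a patient who stopped without switching could remain.

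**Conclusion.** The point holds in a limited form. SAP 2.5.4 item 1 gives the 1-step label to a set that excludes code-1 deviators and places it beside a 3-step set that keeps them, so some 1-step patients appear in neither. The responder rate lacks a FAS 1-step result, although there the set is correctly called per protocol. The narrowed PP definition conflicts with the protocol's permission to switch and is not listed in Section 4.

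The primary analysis uses the whole FAS whatever the regimen and is unaffected, as is the sample size. The affected results are supportive or additional and descriptive. The range of 0.05 to 0.40 points rests wholly on assumed deviation rates and differences, so the actual size cannot be derived from the documents.

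A reader might infer that FAS 1-step beside FAS 3-step would show the effect of titration. It would not: patients reach 3-step through events after baseline, so the groups stay non-comparable. The correction removes one avoidable difference between them. The correction should be made, but restoring the protocol's PP set is a matter of choice.

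**What to change.** 1. In SAP 2.5.4 item 1, the responder analysis in Section 4 point 1, and wherever 2.6.1 applies, present FAS 1-step beside FAS 3-step. Note that both groups are formed after baseline.
2. Report the PP analysis under its own name and not as the 1-step result.
3. Define the FAS 3-step set in SAP 2.2.
4. State in 2.6.1 which endpoints it covers.
5. List the narrowed PP definition in SAP Section 4 and reconcile it, together with S02, with the protocol passages that permit the switch.

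The cost is SAP wording and one extra column per affected table, with the corresponding 2.5.4 figure. The regimen flag is already needed for 2.2.1.1. No new data are required, and neither the primary analysis nor the sample size changes.
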